3.6. Missing Data and Outliers

3.6.1. Missing Data

In general, missing data will not be imputed unless methods for handling missing data are specified. Exceptions are presented in this document.

For missing last dose date of study drug, imputation rules are described in Section 4.2.1. Imputation and calculation rules for missing patient diary data are described in Appendix 4. The handling of missing or incomplete dates for AE onset is described in Section 7.1.5.2 and for prior and concomitant medications in Section 7.4.

3.6.2. Outliers

Outliers will be identified during the data management and data analysis process. All data, including outliers, will be included in the data analyses, unless otherwise specified.

3.7. Data Handling Conventions and Transformations

In general, age (in years) on the date of the first dose of study drug will be used for analyses and presentation in listings. If an enrolled subject was not dosed with any study drug, the randomization date will be used instead of the first dosing date of study drug. For screen failures, the date the informed consent was signed will be used for age calculation. If only birth year is collected on the CRF, “01 July” will be used for the unknown birth day and month for the purpose of age calculation. If only birth year and month are collected, “15” will be used for the unknown birth day.

Duration of UC (years) is the number of years between the diagnosis date of UC and date of first dose of Induction study drug. The partial diagnosis date of UC (if any) will be imputed for calculation as follows:

- If day and month are missing but year is available, then the imputed day and month will be 01 Jan.
- If day is missing but the month and year are available, then the imputed day will be the first day of the month. Partial date will not be imputed if the year is missing.

Non-PK Data that are continuous in nature but are less than the lower limit of quantitation (LOQ) or above the upper LOQ will be imputed as follows:

- A value that is 1 unit less than the LOQ will be used for calculation of descriptive statistics if the datum is reported in the form of “< x” (where x is considered the LOQ). For example, if the values are reported as < 50 and < 5.0, values of 49 and 4.9, respectively, will be used for calculation of summary statistics. An exception to this rule is any value reported as < 1 or < 0.1, etc. For values reported as < 1 or < 0.1, a value of 0.9 or 0.09, respectively, will be used for calculation of summary statistics.

- A value that is 1 unit above the LOQ will be used for calculation of descriptive statistics if the datum is reported in the form of “> x” (where x is considered the LOQ). Values with decimal points will follow the same logic as above.
- The LOQ will be used for calculation of descriptive statistics if the datum is reported in the form of “≤ x” or “≥ x” (where x is considered the LOQ).

Natural logarithm transformation will be used for plasma concentrations and analysis of PK parameters. Plasma concentration values that are below the limit of quantitation (BLQ) will be presented as “BLQ” in the concentration data listing. Values that are BLQ will be treated as 0 at predose time points, and one-half the value of the LOQ at postbaseline time points.

The following conventions will be used for the presentation of summary and order statistics:

- If at least 1 subject has a concentration value of BLQ for the time point, the minimum value will be displayed as “BLQ.”
- If more than 25% of the subjects have a concentration data value of BLQ for a given time point, the minimum and Q1 values will be displayed as “BLQ.”
- If more than 50% of the subjects have a concentration data value of BLQ for a given time point, the minimum, Q1, and median values will be displayed as “BLQ.”
- If more than 75% of the subjects have a concentration data value of BLQ for a given time point, the minimum, Q1, median, and Q3 values will be displayed as “BLQ.”
- If all subjects have concentration data values of BLQ for a given time point, all order statistics (minimum, Q1, median, Q3, and maximum) will be displayed as “BLQ.”

Pharmacokinetic parameters that are BLQ will be imputed as one-half LOQ before log transformation or statistical model fitting.

3.8. Analysis Visit Windows

3.8.1. Definitions

3.8.1.1. Induction Studies (Cohort A Induction Study and Cohort B Induction Study)

The First Dosing Date of each Induction Study is defined as the date when subjects take the first dose of Induction study drug, as recorded in the Study Drug Administration eCRF.

The Last Dosing Date of each Induction Study is defined as the date when subjects take the last dose of Induction study drug as recorded in the Study Drug Administration eCRF.

Study Day will be calculated from the first dosing date of study drug and derived as follows:

- For days on or after first dosing date: Assessment Date - First Dosing Date + 1
- For days prior to the first dosing date: Assessment Date - First Dosing Date

Therefore, Study Day 1 is the day of the first dose of study drug administration.

Baseline is defined as the last available observation on or prior to the first dosing date, unless otherwise specified.

3.8.1.2. Maintenance Study

The First Dosing Date of Maintenance Study is defined as the date when subjects take the first dose of Maintenance Study drug, as recorded in the Study Drug Administration eCRF.

The Last Dosing Date of Maintenance Study is defined as the date when subjects take the last dose of Maintenance study drug as recorded in the Study Drug Administration eCRF.

Maintenance Study Day (M-Day) will be calculated from the First Dosing Date of Maintenance Study and derived as:

- For days on or after First Dosing Date of Maintenance Study: Assessment Date - First Dosing Date + 1
- For days prior to First Dosing Date of Maintenance Study: Assessment Date - First Dosing Date

Therefore, M-Day 1 is the first dosing date of the Maintenance Study.

Re-randomization baseline (henceforth referred to as re-baseline) is defined as the last available observation on or prior to the first dose date of the Maintenance Study. Re-baseline will be considered the baseline of Maintenance Study, unless otherwise specified.

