Week 2	Week 2	15	2	22
Week 4	Week 4	29	23	36
Week 6	Week 6	43	37	57
Week 10	Week 10	71	58	For subjects who entered Maintenance Study: minimum of 85 and Study Day of [Maintenance first dose date]; for other subjects: ≥ 71

Note: ECG, lipid profile, fecal lactoferrin, and fecal calprotectin are collected postbaseline at Weeks 10, 26, and 58 only and the corresponding analysis windows will be applied; serum immunoglobulin is collected postbaseline at Weeks 4, 10, 26, and 58 only and the corresponding analysis windows will be applied.

Table 3-8. Analysis Visit Windows for Maintenance Study Weight, Vital Signs, ECG, Hematology, Chemistry, Lipid Profile, Serum Immunoglobulin, hs-CRP, Fecal Calprotectin and Fecal Lactoferrin

Nominal Visit	Analysis Visit	Nominal Day (M-Day)	Lower Limit (M-Day)	Upper Limit (M-Day)
Week 10/11	Re-Baseline	1	none	1
Week 14	Maintenance Week 3	22	2	43
Week 20	Maintenance Week 9	64	44	85
Week 26	Maintenance Week 15	106	86	134
Week 34	Maintenance Week 23	162	135	190
Week 42	Maintenance Week 31	218	191	246
Week 50	Maintenance Week 39	274	247	302
Week 58	Maintenance Week 47	330	303	≥ 330

Note: ECG, lipid profile, fecal lactoferrin and fecal calprotectin are collected postbaseline at Weeks 10, 26, and 58 only and the corresponding analysis windows will be applied; serum immunoglobulin is collected postbaseline at Weeks 4, 10, 26, and 58 only and the corresponding analysis windows will be applied.

3.8.3. Selection of Data in the Event of Multiple Records in an Analysis Visit Window

Depending on the statistical analysis method, single values may be required for each analysis window. For example, change from baseline by visit usually requires a single value, whereas a time-to-event analysis would not require 1 value per analysis window.

If multiple, valid, nonmissing, continuous measurements exist in an analysis window, records will be chosen based on the following rules if a single value is needed:

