- In general, the baseline/re-baseline value will be the last nonmissing value on or prior to the first dose date of study drug for each individual Induction study, and Maintenance Study, respectively, unless otherwise specified. If multiple measurements occur on the same day, the last nonmissing value prior to the first dose of study drug will be considered as the baseline value. If these multiple measurements occur at the same time or the time is not available, the average of these measurements (for continuous data) will be considered the baseline/re-baseline value.
- For postbaseline visits:

The record closest to the nominal day for that visit will be selected.

If there are 2 records that are equidistant from the nominal day, the later record will be selected.

If there is more than 1 record on the selected day, the average will be taken, unless otherwise specified.

If multiple, valid, nonmissing, categorical measurements exist in an analysis window, records will be chosen based on the following rules if a single value is needed:

- For baseline/re-baseline, the last available record on or prior to the date of the first dose of study drug for each individual study (Cohort A Induction Study, Cohort B Induction Study and Maintenance Study) will be selected. If there are multiple records with the same time or no time recorded on the same day, the value with the lowest severity will be selected (eg, normal will be selected over abnormal for safety ECG findings).
- For postbaseline visits:

The record closest to the nominal day for that visit will be selected.

If there are 2 records that are equidistant from the nominal day, the later record will be selected.

If there is more than 1 record on the selected day, the worst severity will be taken (eg, abnormal will be selected over normal for safety ECG findings), unless otherwise specified.

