6.4.2.2. Analysis of MCS and pMCS exploratory endpoints

For calculation of MCS and pMCS, please refer to rules described under [Section 6.1.1](#) for MCS and pMCS with subscores.

MCS at screening will serve as induction baseline MCS. Partial MCS at Day 1 will serve as induction baseline pMCS. If pMCS at Day 1 is missing, the screening partial MCS will be used as induction baseline.

MCS at Week 10 will serve as maintenance re-baseline MCS. Partial MCS at Maintenance Day 1 will serve as Maintenance re-baseline pMCS. Re-baseline values of MCS and partial MCS will serve as Maintenance Study baseline for change from baseline calculation.

As 2 of the 3 partial MCS components (stool frequency and rectal bleeding) will be collected through the subject daily diary, partial MCS will be calculated at all visits when PGA is scheduled to be assessed.

Descriptive statistics will be used to summarize the absolute values and change from baseline values in MCS, endoscopic subscore, stool frequency subscore, rectal bleeding subscore, PGA and partial MCS by analysis visit and treatment group for Cohort A Induction Study, Cohort B Induction Study, and Maintenance Study. Shift tables of MCS subscores from baseline to Week 10 for Induction Studies and from Week 10 to Week 58 for Maintenance Study will be provided.

Difference of mean change from baseline at Week 10 for Induction Studies and difference of mean change from re-baseline at Week 58 for Maintenance study between each filgotinib dose group and placebo for partial MCS will be tested in an exploratory fashion using an analysis of covariance (ANCOVA) model adjusting for stratification factors and baseline or rebaseline value, respectively. Last Observation Carried Forward (LOCF) approach will be used to impute the missing values. Estimated means of treatment effects and estimated differences in treatment effects between each filgotinib treatment group and the placebo group will be presented with 95% CIs and nominal p-values. Difference of mean change from baseline (or re-baseline) for partial MCS at Weeks 2, 4, and 6 for Induction Studies and at Weeks 14, 20, 26, 34, 42 and 50 for Maintenance Study will be analyzed in the same fashion. The model based estimated mean change from baseline (or re-baseline) with 95% CIs will be plotted over all analysis visits by treatment group.

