6.4.2.3. Analysis of exploratory Health-Related Quality of Life (HRQoL) endpoints

HRQoL questionnaires include Short-Form 36 Health Survey (SF-36), Work Productivity and Activity Impairment questionnaire (WPAI), EuroQoL (health-related quality of life questionnaire) (EQ-5D), and inflammatory bowel disease questionnaire (IBDQ).

HRQoLs will be collected at baseline, Week 10, Week 26, and Week 58.

SF-36

The SF-36 is a health related quality of life instrument consisting of 36 questions belonging to 8 domains in 2 components and covers a 4-week recall period:

- Physical well-being, 4 domains: physical functioning (10 items), role physical (4 items), bodily pain (2 items), and general health perceptions (5 items)
- Mental well-being, 4 domains: vitality (4 items), social functioning (2 items), role emotional (3 items), and mental health (5 items).

The remaining item (health transition) is not part of the above domains but is kept separately. These scales will be rescaled from 0 to 100 (converting the lowest possible score to 0 and the highest possible score to 100), with higher scores indicating a better quality of life. The SF-36 is not disease specific and has been validated in numerous health states.

The change from baseline at Week 10 for Cohort A and B Induction Studies and the change from re-baseline at Weeks 26 and 58 for Maintenance Study in each of the 8 domains and each of the 2 components in SF-36 will be analyzed using an ANCOVA model. The model will include treatment, stratification factors and baseline/re-baseline score as covariates. LOCF approach will be used to impute missing values. Estimated means of treatment effects and estimated differences in treatment effects between each filgotinib treatment group and the placebo group will be presented with 95% CIs and nominal p-values.

Descriptive statistics will be used to summarize the absolute values and change-from baseline (or re-baseline) values for each domain as well as each component by treatment group and analysis visit.

WPAI

The WPAI is a designed to measure the effect of general health and symptom severity on work productivity and regular activities during the past seven days.

The questionnaire consists of 6 questions:

- Q1: currently employed,
- Q2: work time missed due to UC,
- Q3: work time missed due to other reasons,
- Q4: hours actually worked,

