9. BIOMARKER ANALYSIS

The biological marker analysis will be conducted on the Biomarker Analysis Set, defined in Section 3.1.7.

Serum hs-CRP, fecal calprotectin, and fecal lactoferrin will be listed and summarized for Cohort A Induction Study, Cohort B Induction Study, and Maintenance Study separately by treatment using descriptive statistics including baseline (or re-baseline) values, values at each postbaseline time point, change from baseline (or re-baseline) and percent change from baseline (or re-baseline) at each postbaseline time point. The definitions of baseline (or re-baseline) for each study are in Section 3.8.1.

Summaries of fecal calprotectin and serum hs-CRP for subjects who have baseline (or re-baseline) values satisfying the following criteria will also be provided for Cohort A Induction Study, Cohort B Induction study, and Maintenance Study:

- Fecal calprotectin $> 250 \mu\text{g/g}$
- Fecal calprotectin $\leq 250 \mu\text{g/g}$
- hs-CRP $> 3 \text{ mg/L}$
- hs-CRP $\leq 3 \text{ mg/L}$

Mean (Q1, Q3) of the observed change from baseline (or re-baseline) values for fecal calprotectin, fecal lactoferrin, and serum hs-CRP will be plotted by treatment and visit for Cohort A Induction Study, Cohort B Induction Study, and Maintenance Study separately as well.

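### For HRQoL scores and fecal markers, Maintenance re-baseline has no earliest date, so a missing Week 10 value is replaced by a pre-treatment one

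*SAP*

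**What the plan says.** SAP 3.8.1.2 states that re-baseline "is defined as the last available observation on or prior to the first dose date of the Maintenance Study", and adds: "Re-baseline will be considered the baseline of Maintenance Study, unless otherwise specified". SAP 3.8.3 repeats the rule for choosing among records: "the last nonmissing value on or prior to the first dose date of study drug for each individual Induction study, and Maintenance Study". The re-baseline rows name Week 10 (Table 3-6, HRQoL) or Week 10/11 (Table 3-8, which includes the fecal markers), but their lower limit is given as none. The Week 10 rows of the Induction tables (3-5 and 3-7), by contrast, open on Study Day 58.

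On timing, SAP 6.4.2.3 says "HRQoLs will be collected at baseline, Week 10, Week 26, and Week 58". The note to Table 3-7 says "ECG, lipid profile, fecal lactoferrin, and fecal calprotectin are collected postbaseline at Weeks 10, 26, and 58 only". The schedule of assessments places the pre-treatment HRQoL assessment on Day 1 and the pre-treatment fecal sample at screening.

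The rule is used in three places:
- SAP 6.4.2.3 analyses HRQoL change from re-baseline at Weeks 26 and 58, with the re-baseline score as an ANCOVA covariate.
- SAP Section 9 summarises change and percent change from re-baseline for the fecal markers, and splits the calprotectin summaries at 250 µg/g. On the definition it says: "The definitions of baseline (or re-baseline) for each study are in Section 3.8.1".
- SAP 5.2 tabulates the same calprotectin split at re-baseline for the Maintenance FAS.

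SAP 6.4.2.2 is more specific for the Mayo score: "MCS at Week 10 will serve as maintenance re-baseline MCS". It fixes partial MCS to Maintenance Day 1.

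**The concern.** For the six measures there is nothing between the pre-treatment value and Week 10. A subject who qualifies for Maintenance but lacks the Week 10 questionnaire or stool sample is given a re-baseline from active, untreated disease. Nothing in the derivation marks that value as predating Induction.

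Such subjects can enter Maintenance. Protocol 4.5.1 and the Maintenance FAS in SAP 3.1.2 require a Week 10 MCS response or EBS remission, not a questionnaire or stool sample. The Biomarker Analysis Set in SAP 3.1.7 asks for a non-missing baseline and one later value on at least one of three markers, which does not guarantee a Week 10 calprotectin.

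At stake is the reading of the within-arm Maintenance results. Change from re-baseline should show whether the Induction gain was kept. For affected subjects it is the Induction gain plus the Maintenance change, so loss of response looks smaller. In the calprotectin split, a pre-treatment value above 250 µg/g puts the subject in the high group whatever the Week 10 status was, and any Induction fall then appears as a Maintenance fall.

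The fallback looks unintended. Where the SAP wants a screening value as substitute it says so, as for a missing Day 1 partial MCS in 6.4.2.2.

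**Working it through.** The plan states no figure on this point, so there is none to reproduce.

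**1. Does a pre-treatment value qualify?** Take the first Maintenance dose on Study Day 78 (the Week 11 visit) and the M-Day rule in SAP 3.8.1.2 (assessment date minus first Maintenance dose date for earlier days; there is no Day 0):
- Week 10, Study Day 71: 71 − 78 = −7
- Start of the Week 10 window, Study Day 58: 58 − 78 = −20
- Day 1: 1 − 78 = −77
- Screening, Day −1 to Day −30: −78 to −107

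All of these lie in the window from no lower limit to M-Day 1. With Week 10 absent, the last value is Day 1 (HRQoL) or screening (fecal markers).

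**2. Within-arm shift.** Let m be the share of re-randomised subjects with a missing Week 10 value and D the mean Induction change in SD units. Replacing Week 10 by the pre-treatment value adds the subject's Induction change to the change score. If missingness is unrelated to the size of that change, the arm mean shifts by m × D. The documents give neither input; assume m = 2%, 5%, 10% and D = 0.5, 1.0, 1.5 SD. For the roughly 285 subjects per dose comparison planned in SAP 1.3, these shares are about 6, 14 and 29 subjects.

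**3. Effect on the contrast.** Simulation, 600 runs per setting, 190 versus 95 subjects, ANCOVA on change with re-baseline as covariate. All scores have SD 1; the correlation is 0.5 between pre-treatment and Week 10 and between Week 10 and the later score; the true difference is 0.40. Values are missing at random, with no LOCF and no stratification factors.

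| D (SD) | m | Shift m × D (SD) | Contrast without / with substitution | SE ratio |
|---|---|---|---|---|
| 0.5 | 2% | 0.010 | 0.393 / 0.392 | 1.004 |
| 0.5 | 5% | 0.025 | 0.401 / 0.401 | 1.010 |
| 0.5 | 10% | 0.050 | 0.405 / 0.404 | 1.020 |
| 1.0 | 2% | 0.020 | 0.399 / 0.399 | 1.006 |
| 1.0 | 5% | 0.050 | 0.393 / 0.392 | 1.015 |
| 1.0 | 10% | 0.100 | 0.399 / 0.400 | 1.028 |
| 1.5 | 2% | 0.030 | 0.402 / 0.402 | 1.011 |
| 1.5 | 5% | 0.075 | 0.406 / 0.405 | 1.023 |
| 1.5 | 10% | 0.150 | 0.399 / 0.398 | 1.040 |

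Simulated shifts agree with m × D to within 0.002. The contrast is unmoved because the re-baseline value, substituted or not, is fixed before re-randomisation.

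**4. Calprotectin category, illustration only.** If a proportion h of responders exceed 250 µg/g at Week 10 and p exceeded it at screening, the share of the high group that rests on a pre-treatment value is m·p / [(1 − m)·h + m·p]. Both proportions are assumptions:
- h = 40%, p = 85%: 4.2%, 10.1%, 19.1% at m = 2%, 5%, 10%
- h = 60%, p = 75%: 2.5%, 6.2%, 12.2%

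Some of these subjects would also have been above 250 at Week 10, so this is not a misclassification rate.

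**The case against.** The strongest reply is that nothing confirmatory depends on this. EBS remission at both time points uses screening subscores (SAP 6.2.1), and the key secondary endpoints are states at Week 10 or Week 58. Re-baseline does enter the CMH strata and the corticosteroid-free endpoint, but as medication use, not as a visit assessment that can fall back. HRQoL testing is exploratory (SAP 6.4) and Section 9 is descriptive. All of this stands.

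A reader might infer that the Maintenance treatment comparison is biased. It is not in expectation: a missing Week 10 value precedes re-randomisation and cannot depend on the Maintenance arm.

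A reader might also take the fault to cover every re-baseline measure. The documents do not support that:
- Hematology, chemistry, hs-CRP, weight and vital signs are also taken at Weeks 2, 4 and 6, and immunoglobulin at Week 4, so the usual fallback is on treatment.
- MCS and partial MCS have their own rule. The MCS subscore shift tables run from Week 10, and the Week 10 endoscopic subscore is needed to qualify for the Maintenance FAS.
- Geboes has no planned change from re-baseline, and its item in SAP 5.2 is Week 10 status.
- The calprotectin and hs-CRP subgroups for the primary endpoint (SAP 6.2.5) use Induction baseline.

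Lipids and ECG do share the schedule gap. For lipids, however, a cut-off carries a cost: under SAP 7.2.2.1 a missing re-baseline makes any Grade 1 or higher laboratory value treatment emergent, and under 7.2.2.2 any Grade 3 or 4 value marked. For ECG, SAP 7.5 drops the subject from the shift-table denominator. Extending the limit to all of Table 3-8 would also discard usable Week 6 values.

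Finally, Week 10 missingness may be low, since these assessments are scheduled at the visit that decides eligibility. That limits the size of the problem but does not make the rule right.

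**Conclusion.** The point holds for SF-36, WPAI, EQ-5D, IBDQ, fecal calprotectin and fecal lactoferrin. Followed as written, the SAP uses a pre-Induction value as Maintenance baseline whenever Week 10 is missing. Within-arm change from re-baseline and the calprotectin split at re-baseline then carry the Induction effect for those subjects. This is a stated rule with an unwanted result, not an absent detail.

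The size is modest: a within-arm shift of 0.01 to 0.15 SD and a standard error increase of about 0.4–4%, under the assumed 2–10% missing and 0.5–1.5 SD Induction change. The calprotectin shares rest on further assumed proportions and show only that the effect on a category can be larger than on a mean. No primary or key secondary result changes. The correction is still worth making, because the within-arm tables would be read as maintenance of response and the substitution is invisible in them.

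**What to change.** In SAP 3.8.1.2 and 3.8.3, and by note to Tables 3-6 and 3-8, state for these six measures only that the re-baseline value must fall on Study Day 58 or later, up to the first Maintenance dose. Give the limit in Study Days, because those tables run on M-Day. With no value in that window, re-baseline is missing and the subject is left out of change-from-re-baseline summaries and re-baseline categories.

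In the HRQoL ANCOVA, keep such subjects: model the Week 26 or Week 58 score as outcome, and fill the missing re-baseline covariate with the overall mean, the same for both arms. Where re-baseline is observed for everyone, this gives the same treatment contrast as modelling change, since the covariate is already in the model. A common fill value is acceptable because re-baseline precedes re-randomisation.

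Do not apply the Day 58 limit to hematology, chemistry, lipids, immunoglobulin, hs-CRP, weight or vital signs. Most have on-treatment fallbacks, and the missing-baseline rules in SAP 7.2.2 would create spurious laboratory abnormalities. The pre-treatment fallback for lipids stays as the lesser problem.

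The cost is a few lines of SAP text, one derivation condition and a small change to the HRQoL model. Subjects without a Week 10 value lose a change score in exploratory descriptive tables.
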